6.2.4 Biomarkers

Research samples (3 mL of blood for exploratory analysis (including cytokine analysis), 10 mL blood to generate plasma (for analysis of SARS-CoV-2 viral load) and 2.5 mL blood in Paxgene tubes (optimized for analysis of gene expression (RNA), and saliva samples (5mL) and/or nasopharyngeal swab for viral titer will be obtained as a part of this clinical trial to better understand SARS-CoV-2 pathogenesis and responses to tofacitinib compared to SOC. Whole blood (10 mL) may also be collected as available for lymphocyte subset analysis by flow cytometry. Sample collection times are specified in the Schedule of Activities. All research blood samples may be banked and/or used for exploratory analysis related to COVID-19 and/or the mechanism of action of the treatments administered in this study. Detailed sample collection and processing instructions will be provided under separate cover. Changes in research-based parameters will be documented.

The results will not be relayed to the subject or the subject's physician because they are for research purposes and the results may not be known for weeks after hospitalization. No results will be entered into the subject's medical record.

6.3 Study Procedures

6.3.1 Study Schedule

Visit Identifier ^{Error!} Reference source not found.	Screening	Day 1	Daily assessments (days 2-14) ^{c,d}	Early Termination/ Discontinuation/ End of Treatment (Day 14 or Discharge)	Follow-up ^{Erro} r! Reference source not found. (Dav 28)	Follow-up (Day 60)	Follow up (Day 90)	Early Termination/ Discontinuation
Visit Window	48 hours prior				+/-3 days			
	to Day 1							
Informed consent	х							-
Medical history	х							
Physical examination ^d	х	х	х	Х	Х			
Weight ^d	Х							
Vital signs ^d (pulse, blood pressure, respiratory rate ^e , temperature ^f)	Х	×		X	Х			
Laboratorv ^d			х					
Hematology	X		X		N N			
	X	X	Χ	X	X			
Blood chemistry	х	х	Х	Х	х			
Coagulation ^g	Х	х	х	Х	х			
Inflammation panel ^h	х	х	х	Х	Х			
Cardiac panel ⁱ	х	х	х	Х	х			
Pregnancy test	Х				Х			
Oxygen saturation by pulse oximetry (SaO ₂) ^d	Х	х	х	Х	Х			
12 Lead ECG ^d	Х	х	х	Х	Х			
Record if admitted to intensive care unit (ICU)	Х	х	х	Х	х			х
Registration/randomization		х						
Study drug administration		х	х	Х				
NIAIA Ordinal scale of disease severity	х	х	х	Х	х	х	х	х

APPROVED BY THE YALE UNIVERSITY IRB 9/28/2020

Protocol 2000027848

Version R5; 15 SEPTEMBER 2020

Visit IdentifierError! Reference source not found.	Screening	Day 1	Daily assessments (days 2-14) ^{c,d}	Early Termination/ Discontinuation/ End of Treatment (Day 14 or Discharge)	Follow-up ^{Erro} r! Reference source not found. (Day 28)	Follow-up (Day 60)	Follow up (Day 90)	Early Termination/ Discontinuation
Visit Window	48 hours prior				+/-3 days			
	to Day 1							
Record hospitalization status	х	х	х	Х	х	х	х	х
Assessment signs and symptoms of pneumonia		х		Х	х	х	х	
FiO2	х	х	х	х				
supplemental oxygen	х	х	х	х				
Blood for exploratory analysis ⁱ		х	Day 7	х	х			
Paxgene sample for exploratory biomarker analysis ^k		х	Day 7	х				
Plasma, Saliva and/or nasal swab for SARS-CoV-2 and exploratory analysis ^m		х	Day 7	х				
Whole blood for FACS analysis ⁿ		х	Day 7	х	x			
Concomitant treatment(s)		Х	Х	Х	X			Х
Adverse event monitoring	Х	Х	Х	Х	×	Х	Х	X□

Visit Identifier ^{Error! Reference source} not found.	Screening	Day 1	Daily assessments (days 2-14) ^{c,d}	Early Termination/ Discontinuation/ End of Treatment (Day 14	Follow-up ^{Erro} r! Reference source not found.	Follow-up (Day 60)	Follow up (Day 90)	Early Termination/ Discontinuation
Visit Window	48 hours prior to Day 1			or Discharge)	(Day 28) +/-3 days			

a. Day relative to start of study intervention (Day 1).

- b. Contact may occur via telephone contact and will occur up to 90 days from administration of the final dose of study intervention. Procedures listed for Follow-up Visit 1 (with exception of ordinal scale of disease severity, hospitalization status, supplemental oxygen/ventilatory support status, contraception check, concomitant medications, and AE/SAE monitoring) will only be performed if the participant is hospitalized. Otherwise these visits will be remote phone or telemedicine visits.
- c. Assessments will be performed at least daily while hospitalized by the clinical service. Vital signs may be more frequent (eg, every 4 8 hours), per hospital practice.
- d. Collected as per hospital standard of care practice
- e. Note if spontaneous or mechanical ventilator setting
- f. Note if oral, rectal, or core

L

- g. Will include PT/PTT, fibrinogen, D-Dimers
- h. Inflammation will include as available: hsCRP, ferritin, procalcitonin, fibrinogen, LDH, etc.
- i. Cardiac panel will include as available: high sensitivity troponin, BNP, etc.
- j. Cytokine panel will include, as available: IL-1, IL-2, IL-6, IL-8, IL-17A, IL-17F, TNF-α, IP-10, IFNγ, CCL5, etc. Sample will be used for cytokine assessment that may include but is not limited to IFNγ, IL-1β, IL-4, IL-6, IL-10, IL-12p70, TNFa, IP-10, and IL-2R. This sample may also be banked and/or used for additional post-hoc analyses related to COVID-19 and/or the mechanism of action of treatments administered in this study, including IgG and IgM antibodies to COVID-19.
- k. Paxgene sample (optimized for RNA analysis) may be banked and/or used for exploratory assessments related to COVID-19 and/or the mechanism of action of treatments administered in this study.
 - Physical examination by a clinician will be individualized according to participant status
- m. Plasma, saliva and/or nasal swab will be collected and tested for SAR-CoV2 should by performed by polymerase chain reaction (PCR), or other commercial or public health assay in any specimen prior to randomization and on an ongoing basis, as needed for patient care and per policy at YNHH. Samples may also be used for additional analyses related to COVID-19 and/or the mechanism of action of treatments administered in this study.
- n. Whole blood sample may be collected as available for analysis of lymphocyte subsets by flow cytometry.

6.3.2 Informed Consent

Potential subjects will be identified by study coordinators in conjunction with treating clinicians by screening the EMR of patients with a clinical diagnosis of SARS-CoV-2. Patients whose providers feel they are appropriate for the study will be approached. The PI or study coordinator will first approach the patient's treating clinician (ex: physician, nurse practitioner, or physician's assistant) regarding possible involvement in the study. If the provider feels the patient is appropriate, they will ask if the patient would be interested in hearing about a research project they might be able to participate in. If the patient expresses interest, the PI or study coordinator will then discuss with the patient.

The patient or legally authorized representative/surrogate will be offered participation in the study during their hospitalization. Proper written, informed consent and HIPAA authorization will be obtained prior to patient participation in this trial. Patients will be provided with an unsigned consent form by a health care worker who has entered their room, and notified that a member of the study team will discuss the protocol with them over phone/video call. The overall protocol (including objectives, procedures and duration), potential risks and benefits, voluntary nature and ability to withdraw will be

discussed with each patient and/or their legally authorized representative/surrogate. The patient and/or their legally authorized representative/surrogate will have all questions answered before being asked to sign the ICF. Verification of comprehension of the consent will be obtained by asking the subject to describe in their words the purpose and risks of the study. The patient and/or their legally authorized representative/surrogate will be instructed that his or her care will not be affected by his or her decision to participate, or not. If the patient and/or their legally authorized representative/surrogate voluntarily agrees to participate in the trial, he or she will be asked to sign the ICF. The subject and/or their legally authorized representation form signed by them. Due to contamination of the document by infectious material, a photograph of the informed consent document with attestation by the person entering the photograph into the study record that states how that photograph was obtained and that it is a photograph of the informed consent signed by the patient will be added to the patient's study records as documentation that the patient signed the informed consent document (in accordance with FDA-2020-D-1106).

6.3.3 Screening

The screening visit will include the following assessments:

- Informed consent
- Medical history: includes collecting the following information: age, sex, race, medical comorbidities, medications, smoking and alcohol history, and family history
- Vital signs, weight, and pulse oximetry
- Targeted physical exam including an assessment of lungs, heart, circulation/perfusion
- Chest X-ray (CXR)
- Electrocardiogram (ECG)
- Blood and urine laboratory tests including lactate dehydrogenase (LDH), complete blood count with differential (CBC), comprehensive metabolic panel (CMP), cytokine panel, cardiac panel, coagulation, inflammation panel, viral serologies (including SARS-CoV-2), tuberculosis testing, and urinalysis
- Urine pregnancy testing and contraception check for women of childbearing potential

6.3.4 Enrollment

After Screening, if the subject meets criteria, they will be enrolled. Baseline labs including hsCRP, ferritin, LDH, D-dimer, CBC, and CMP will be measured twice daily (per SOC). Research blood samples will be obtained prior to drug administration on Day 1 and then again on Day 2 and every 48 hours thereafter. All subjects will be randomized to either tofacitinib 10 mg twice daily or SOC. Patients will be monitored at least once daily after initiation of therapy during the duration of their hospitalization, and will be followed up after discharge.

6.3.5 On Study Visits

Days 1-14:

Once eligibility is confirmed, patients will be randomly assigned to receive treatment with either tofacitinib or placebo. Patients will receive 10 mg tofacitinib orally twice daily starting at the time of study enrollment until they exhibit clinical improvement, as

defined by need for supplemental oxygen to the baseline level. After this, patients will receive 5 mg tofacitinib orally twice daily. Total tofacitinib treatment duration will not exceed 14 days. All dosing of study drug will be in addition to current standard of care treatment. Research blood samples will be obtained prior to drug administration and again every 48 hours. Patients may undergo additional viral testing with a repeat nasal swab and/or blood collection at 7 and 14 days after enrollment. Standard of care laboratory tests will be measured twice daily. Patients will be assessed daily while hospitalized for the following clinical, research, and laboratory parameters:

- Targeted physical exam
- Electrocardiogram (ECG)
- Blood and urine laboratory tests including lactate dehydrogenase (LDH), complete blood count with differential (CBC), comprehensive metabolic panel (CMP), cytokine panel, cardiac panel, coagulation, inflammation panel, and urinalysis
- Adverse events
- Concomitant therapies
- Record of ICU admission
- Record use of supplemental oxygen

6.3.6 End of Study and Follow-up

After patients complete study treatment, they will be contacted to follow up on their condition. This may occur via telephone or telehealth and will occur on day 28 +/- 3 days after the time of enrollment and then again at days 60 and 90 days. On day 28 follow-up, blood sample for exploratory analysis may be collected. At the time of follow up visits/calls, patients will be asked about:

- Adverse events
- Concomitant therapies
- All efforts will be made to contact subjects for follow-up, including: telephone calls, texts, and emails to the subject and/or close contacts. Vital status of all subjects will be ascertained either by contacting the subjects and/or subjects' close contacts or by a vital records search.

6.3.7 Removal of subjects

Required Tofacitinib Discontinuations:

- White blood cell count < 1000 cells/mm3
- Lymphocyte counts <250 cells/mm3.
- Absolute neutrophil counts <500 cells/mm3.
- Hemoglobin less than 8 g/dL.
- ALT or AST ≥5 times the ULN.
- Anaphylaxis or other serious allergic reaction.
- Diagnosis of thrombosis including pulmonary embolism, deep venous thrombosis, and arterial thrombosis.
- Diagnosis of venous thromboembolism.
- Any serious infection, including secondary bacterial pneumonia, or other safety event for which the investigator determines that continued treatment with tofacitinib is not in the participant's best interest.

 If IL-6 targeting agent or other non-FDA approved, compassionate use or expanded access is considered as medically necessary (as reviewed by the investigator)

Subjects who discontinue study treatment will be followed up through Day 90 after discontinuation.

6.4 Statistical Method

6.4.1 Statistical Design

6.4.2 Sample Size Considerations

Assume true probability of a participant survived and not needing any form of mechanical ventilation, high flow oxygen, or ECMO at day 14 is 40%. Randomizing 60 participants with a 1:1 ratio (tofacitinib+SOC: Placebo+SOC), the study will have 73% power (two-sided alpha=0.1) assuming an odds ratio of 3.5 for tofacitinib+SOC VS Placebo+SOC. No multiplicity adjustments will be performed for any secondary endpoint or exploratory endpoint analyses.

6.5 Planned Analyses

There will be two analyses for reporting results from this study. The first will occur when all patients have completed the requirements for the day 14 efficacy endpoints, including the primary endpoint. This will be the primary analysis for these endpoints. The second will be after all participants have completed the 90 day follow-up where mortality and final safety will be reported.

The SAP may modify what is outlined in the protocol where appropriate; however, any major modifications of the primary endpoint definitions or their analyses will also be reflected in a protocol amendment.

6.5.1 Primary Objective Analysis

Proportion of subjects alive, not needing any form of mechanical ventilation, high flow oxygen, or ECMO, and haven't received a recue therapy at day 14, will be summarized by treatment arm. Treatment comparisons will be based on a logistic regression model. Odds ratio with 90% confidence interval will be presented.

Full Analysis Set (FAS) is defined as all randomized participants receiving at least one dose of study intervention. Participants will be analyzed according to the intervention to which they were randomized. Efficacy analysis will be based on FAS.

For all primary analyses, data will be censored after subject received rescue therapy. Rescue therapy is defined as IL-6 targeting agent or other non-FDA approved, compassionate use or expanded access is considered as medically necessary (AS REVIEWED BY THE PI) (section 6.1.2). Per protocol, subjects will discontinue from study treatment prior to taking rescue therapy. Additional secondary analyses may be conducted including all the data after rescue therapy.

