Guidance on the management of COVID-19 coagulopathies based on commonly available laboratory tests has been recently published by the ISTH. They found a high incidence of both severe pneumonia and lymphopenia related to COVID-19 infection in patients requiring hospitalization. In this setting, patients with increased D-dimers (3 to 4-fold increase) are more likely to die from COVID-19 infection. Subtle prolongation of prothrombin time is seen in these patients and may be prognostic of mortality. Thrombocytopenia is also seen in these patients but does not seem to be a consistent prognosticator. In addition to monitoring of Ddimer, PT, and platelet counts, the ISTH also recommends monitoring of serum fibrinogen as patients with COVID -19 infection may develop DIC as early as Day 4.

ISTH recommends a prophylactic dosing of LMWH in hospitalized subjects who have COVID-19 infection to protect against sepsis-like coagulopathies and venous thromboembolism in the absence of active bleeding or a platelet count of <25,000 cells/mm³.

Concomitant Therapy

All participants must receive pharmacologic thromboprophylaxis with LMWH and supportive care for COVID-19 pneumonia. Therapies currently being evaluated for treatment of COVID-19 patients have multiple mechanisms of action and address different therapeutic targets. With the exception of EUAs granted by FDA, there are currently no drugs or other therapeutics approved by health/ regulatory authorities to prevent or treat COVID-19 or the severe ARDS it may cause, so it is expected that adjunctive SOC may include investigational and off-label treatments. Some of these therapies are prohibited concomitant medications with tofacitinib; others can be co- administered. Table below lists known

investigational products in clinical trials and drugs that might be administered off-label. In addition, there may be additional products that may be added to the institutional standard of care, for which tofacitinib dosage may need to be adjusted. Treatments that should not be co-administered with tofacitinib during the conduct of this study are identified. If there is any uncertainty about the concomitant use of a treatment with tofacitinib, contact the sponsor.

Investigational and Off-Label Treatments for COVID-19

Category	Treatment	Anticipated Target	Concomitant Use with Tofacitinib

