Antiviral	Remdesivir	Stops virus from replicating; does not interfere with cytochrome P450 metabolism. Approved by FDA for emergency use.	Not prohibited
Antimalarial	Hydroxychloroquine/ chloroquine	Used for the treatment of malaria; anecdotal data. FDA does not recommend use except in clinical trials.	Not prohibited
Azalide Antibiotic	Azithromycin	Has not been used for viral infections; may have some anti-inflammatory action. NIH advised against use of the combination of hydroxychloroquine and azithromycin.	Not prohibited
Antiviral	Combination of lopinavir and ritonavir (Kaletra)	Indicated for treatment of HIV. One study did not show efficacy, but other clinical trials are ongoing.	Requires 50% reduction in dose
Host Modifiers/ Immune-based Therapy	Convalescent plasma	FDA has allowed this to be used in patients with serious or life-threatening COVID-19 infections. This treatment is still considered experimental.	Not prohibited
Host Modifiers/ Immune-based Therapy	Hyperimmune immunoglobulin	Manufactured from convalescent plasma and is allowed to be used in the same population. This treatment is still considered experimental.	Not prohibited
IL-6 Inhibitor	Tocilizumab	Used to treat autoimmune conditions through inhibition of IL-6 and is in clinical trials for COVID to treat hyperinflammation.	Prohibited
IL-6 Inhibitor	Sarilumab	Similar to tocilizumab and is in clinical trials for COVID.	Prohibited
IL-6 Inhibitor	Siltuximab	Similar to tocilizumab and is in clinical trials for COVID.	Prohibited
IL-1 Inhibitor	Anakinra	Used to treat autoimmune conditions through inhibition of IL-1 and is in clinical trials for COVID to treat hyperinflammation.	Prohibited
Janus kinase Inhibitor	Baricitinib	JAK 2 selective inhibitor with ant- iinflammatory properties is in clinical trials for COVID.	Prohibited

Janus kinase Inhibitor	Tofacitinib	JAK 1/ JAK 3 selective inhibitor with anti-inflammatory properties is in clinical trials for COVID.	This is the compound being studied. Additional treatment is
			prohibited.

Modified from the NIH Coronavirus Disease 2019 (COVID-19) Treatment Guidelines https://www.covid19treatmentguidelines.nih.gov/

To the extent possible, the following restrictions should be followed:

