6.1 Treatment

6.1.1 Identity of Investigational Product

Tofacitinib is an orally administered, synthetic small molecule that selectively inhibits the JAK family of kinases, and is currently FDA approved for the treatment of rheumatoid arthritis (RA), psoriatic arthritis (PsA), and ulcerative colitis (UC). Unlike targeted biologic therapies, which are directed at extracellular targets such as individual soluble cytokines (e.g. TNF- α), cytokine receptors (IL-1R, IL-6R) or other cell surface receptors (CD20, CD80, and CD86), tofacitinib works intracellularly⁹ and has been developed to target a number of cytokines known to have a role in inflammatory diseases.

SOC will be determined by YNHH SARS-CoV-2 Therapeutics Group and may include treatment targeting SARS-CoV-2 (e.g., anti-viral therapies). However, those enrolled in our study will not receive other forms of IL-6 blocking agents (e.g. tocilizumab, sarilumab, or other JAKi), if these are part of the SOC algorithm (Please see **Appendix 1** for current algorithm).

Study intervention is defined as any investigational intervention(s), marketed product(s), placebo, medical device(s), or study procedure(s) intended to be administered to a study participant according to the study protocol.

For the purposes of this protocol, study intervention refers to Tofacitinib 5 mg tablets.

All participants will receive pharmacologic thromboprophylaxis with LMWH and supportive care for COVID-19 pneumonia. It is acceptable for participants to also receive experimental therapies for COVID-19, with the exception of prohibited medications listed in the eligibility criteria and concomitant medications sections of the protocol.

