- If IL-6 targeting agent or other non-FDA approved, compassionate use or expanded access is considered as medically necessary (AS REVIEWED BY THE PI)
- Diagnosis of thrombosis including pulmonary embolism, deep venous thrombosis, and arterial thrombosis

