#### **6.4.4. Concomitant Medications and Nondrug Treatments**

Prior treatment are the ones stopped prior to Day 1 of study treatment. Concomitant treatments are the ones taken on Day 1 or after. Prior drug and non-drug treatment, concomitant drug (including SoC) and non-drug treatment will be summarized by treatment group. Number and percent of subjects used additional immunomodulatory agent (i.e., IL-6 targeting therapy), or other non-FDA approved, compassionate use or expanded access treatment will be reported by treatment group.

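### The rescue definition contradicts the protocol's own list of permitted and prohibited COVID-19 treatments: under protocol 6.5.1 permitted care can count as rescue, though the SAP v2.0 primary proportion is unaffected

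*Protocol*

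**What the plan says.** **Rescue and discontinuation.** Protocol 6.5.1 adds absence of rescue by day 14 to the conditions for primary success. It then says: "Rescue therapy is defined as IL-6 targeting agent or other non-FDA approved, compassionate use or expanded access is considered as medically necessary", subject to review by the PI. Protocol 6.1.2 lists the same circumstance among the reasons for permanently stopping study drug: "If IL-6 targeting agent or other non-FDA approved, compassionate use or expanded access is considered as medically necessary (AS REVIEWED BY THE PI". Section 6.3.7 repeats this, with the investigator as reviewer.

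**Concomitant care.** Protocol 5.3.2 says of standard care that "it is expected that adjunctive SOC may include investigational and off-label treatments". Section 6.1.1 says: "It is acceptable for participants to also receive experimental therapies for COVID-19, with the exception of prohibited medications listed in the eligibility criteria", and 6.1.11 says much the same. The 5.3.2 table marks convalescent plasma and hyperimmune immunoglobulin as not prohibited, and says of each: "This treatment is still considered experimental". It marks the IL-6 inhibitors, anakinra, baricitinib and additional tofacitinib as prohibited.

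**SAP v2.0.** Section 2.3 repeats the rescue definition. Section 2.2.1 adopts a treatment policy estimand and names receipt of rescue as an intercurrent event. The primary endpoint in 3.1 and 6.1 has no rescue component, and 5.1 rules out hypothesis testing. Section 6.4.4 says that the number and percentage of subjects given an additional immunomodulatory agent "or other non-FDA approved, compassionate use or expanded access treatment will be reported by treatment group".

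**The concern.** One phrase does three jobs: it stops study drug, it identifies an intercurrent event, and in protocol 6.5.1 it decides whether a patient can be a primary success. It is worded by regulatory status, whereas the protocol's list of what may be given with tofacitinib is worded agent by agent. If the two do not line up, a patient given plasma on Day 2 may continue study drug under the 5.3.2 table, yet must stop and be recorded as rescued under 6.1.2 and 6.5.1. In the other direction, a patient given a prohibited agent might not be recorded as rescued at all. A rescue count built on this phrase then has no stable meaning, and two sites of judgement, or the same one on two days, could code the same treatment differently.

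**Working it through.** No formula decides this point. The check is whether any reading of the phrase reproduces the 5.3.2 table.

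**Step 1: two readings of non-FDA approved.** Reading A takes it as a property of the product, so that approval for any use takes an agent outside the phrase. Reading B takes it as not approved for COVID-19. IL-6 agents are covered by name under both.

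| Agent | 5.3.2 table | Reading A | Reading B |
|---|---|---|---|
| Convalescent plasma | not prohibited | covered (described as experimental) | covered |
| Hyperimmune immunoglobulin | not prohibited | covered (described as experimental) | covered |
| Hydroxychloroquine, azithromycin | not prohibited | not clearly covered | covered |
| Lopinavir/ritonavir | allowed with a dose change | not clearly covered | covered |
| Tocilizumab, sarilumab, siltuximab | prohibited | covered as IL-6 agents | covered as IL-6 agents |
| Anakinra | prohibited | not clearly covered: an IL-1 agent used in other conditions, approval status not stated | covered |
| Additional tofacitinib | prohibited | not clearly covered: 6.1.1 says it is FDA approved for three other diseases | covered |

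Reading A sweeps in two permitted treatments and may miss two prohibited ones. Reading B captures the prohibited agents, but takes in every permitted agent in these rows as well. Neither matches the table.

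**Step 2: does PI review resolve it?** The clause names a reviewer and a test of medical necessity. It gives no rule for separating permitted experimental care from rescue, so the boundary is left to individual cases.

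**Step 3: what happens to a patient labelled as rescued under the protocol?** The first sentence of 6.5.1 makes the patient a non-success. The third paragraph of 6.5.1 says data are censored after rescue. Section 6.5.10 treats binary values with no other information as successes. The label can therefore lead to failure, to a missing value or to success. The primary endpoint in the Synopsis, 4.2 and 5.2.1 has no rescue term.

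**Step 4: what happens under SAP v2.0?** All observed data count whatever intercurrent event occurs (2.2.1), and rescue is not part of the endpoint (3.1, 6.1). Reclassifying a patient as rescued or not rescued changes the SAP primary proportion by zero.

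**Step 5: size if the 6.5.1 composite is reported.** SAP 7 says 24 subjects had been randomized at the only safety review and that no more were enrolled. Arm sizes are not given, so take both stated ratios and assume all 24 are analysed:
- 1:1 (protocol: "Randomizing 60 participants with a 1:1 ratio"): 24/2 = 12 per arm, and one patient is 1/12 = 8.3 percentage points.
- 2:1 (SAP 2.3): 16 and 8 per arm, and one patient is 1/16 = 6.25 or 1/8 = 12.5 percentage points.

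**The case against.** The strongest reply is that SAP v2.0 has already removed the consequence for the primary result. That stands. Protocol 6.5 lets the SAP modify the protocol analysis. It also says major changes to the primary endpoint or its analysis will be reflected in a protocol amendment. None is among the documents supplied, so the 6.5.1 text has not been visibly withdrawn.

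A second reply is that the specific permission in 6.1.1, 6.1.11 and the table should control the general phrase, with PI review filtering out permitted care. That is a sensible reading, but the protocol does not state it, and 6.1.2 presents the trigger as a required discontinuation.

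A reader might infer more than the documents support:
- **A loss of power.** Scoring permitted care as failure would pull the arms together. But the documents give no share of patients receiving such care, the treatment algorithm is an attachment not supplied, and SAP 5.1 plans no test.
- **A flat rule that rescue equals failure.** Step 3 shows that the protocol does not settle this.
- **Remdesivir as a further example.** The table describes it as FDA approved for emergency use, and 5.3.2 sets emergency authorizations apart, so it is not clearly within the phrase.
- **Baricitinib as a prohibited agent that is missed.** Section 6.1.1 groups other JAK inhibitors with IL-6 blocking agents, so it may be covered. That wording could be stretched to additional tofacitinib too, which is why the claim here is only that coverage is unclear.
- **An SAP count that cannot measure rescue at all.** IL-6 intervention is a separate secondary endpoint (SAP 2.2, 3.2), and 6.4.4 can be read as two counts rather than one.

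**Conclusion.** The point holds as a contradiction in the text. The rescue and discontinuation phrase does not agree with the protocol's concomitant-therapy rules on any reading examined. Plasma and hyperimmune immunoglobulin show this most plainly; anakinra and additional tofacitinib show that coverage of prohibited agents is unclear.

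Under protocol 6.5.1, permitted care can be scored as rescue and primary non-success, although the same section also says censored. Under SAP v2.0 the primary proportion does not change. Three effects remain: a discontinuation instruction that conflicts with permitted use, an intercurrent-event label without fixed content, and a 6.4.4 count that can mix prohibited rescue with permitted care.

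The 6 to 12.5 point range applies only to a reported 6.5.1 composite. It assumes 24 analysed patients and one of the two stated ratios. How many patients received any of these agents is not in the documents. If PI review excluded every permitted therapy and captured every prohibited one, the practical effect would be zero.

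**What to change.** 1. The sponsor must reconcile protocol 6.1.2 and 6.3.7 with the 5.3.2 table, 6.1.1 and 6.1.11. No clinical rule is proposed here.
2. In protocol 6.5.1, SAP 2.3 and SAP 6.4.4, replace the phrase with a named list of agents consistent with the reconciled text. State how to classify agents that are not in the table and entries that carry neither label, such as lopinavir/ritonavir. Do the coding without reference to treatment assignment.
3. Report the SAP 6.4.4 count separately for agents the table marks as prohibited and as not prohibited.
4. If the protocol 6.5.1 composite is reported at all, show it under both classifications. This is not needed for the SAP primary proportion, which would be the same either way.

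The cost is wording, some coding of concomitant medications and one extra table row. No new data are needed, because 5.3.2 and 6.1.11 already require all concomitant treatments to be recorded.
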